5.2. Statistical Plan

Measurements made through clinical standard of care will be compared to the measurements recorded by the wearable sensors. Distribution checks for normality and data accuracy will be completed for each individual and for the entire study prior to all analyses. For continuous measures of physiology, 30 second epochs will be defined for each method for comparison. For non-continuous CB-BP measures, each measure will be matched and compared to the 30-second epoch during which the measure was captured. We will further check for time lags in the relationships between methods by applying peak-picking methods to lagged regression plots for all pairs of measures.

Agreement and correlation of wearable sensor measures to standard of care measures will be assessed in two ways. First, Bland-Altman plots will be created to assess agreement between each measurement system via bias and precision, which reflect the mean or average difference between two methods and the variation in these differences, respectively. Our second method consists of individual correlations between methods assessed for each person. This correlational method will supplement additional methods, and can be directly transformed to variance shared between wearable sensor and standard of care measures, a common metric of reliability of any measure.

Formal tests of bias, precision, and correlations: While the above methods will yield useful statistics, they need to be extended to deal with the structured nature of our data. Specifically, our data are clustered, meaning that we have multiple observations within each person and multiple people in our sample, which violates standard independence assumptions inherent to many models. We propose to estimate bias and correlation/reliability using multi-level models, which yield the same statistics discussed above but account for the fact that observations taken from the same patient are more related than comparisons involving different patients.

Statistical power: The large amount of within-person data provides incredibly high statistical power for all planned and many secondary data analyses, allowing this data set to answer all proposed questions. Previous work on power in multilevel models found greater than 99% power to detect associations with the planned observations suggested here within comparable nested designs.

6. References

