optimize these devices for use in pediatric ICU patients, 2) demonstrate safety, reliability, and accuracy of these devices for continuous ICU hemodynamic signal measurements, including but not limited to BP, heart rate (HR), cerebral blood flow, temperature, and respiratory rate, and 3) demonstrate these devices are preferred by patients and parents to current measurement tools. Once validated, such sensors could fundamentally change the way patients are monitored in the ICU, eliminating risks associated with invasive monitoring, allowing continuous, real-time detection of clinically meaningful changes in ICU patients, advancing knowledge of hemodynamic signatures preceding clinically meaningful events, and ultimately offering opportunity to reduce morbidity and mortality in ICU patients.

[figure not shown]

Figure 2: Example of physiology measurements using wearable sensor. (A) ECG time waveforms for commercial cardiac monitoring device (red) and wearable sensor (blue). (B) Snapshot of average heart rate vs time using conventional ECG sensor (control) and wearable sensor in newborn. (C) Snapshot of oxygen saturation vs time using wearable sensor and standard oximetry sensor (control) in newborn. (D) PPG (blue) and ECG (red) waveforms captured simultaneously and synchronized in time in healthy adult subject. Pulse arrival time (PAT) interval denoted in the waveform. (E) Pulse arrival time measurements during rest, Valsalva maneuver and release in adult subject. (F) Correlation of systolic blood pressure (measured with cuff-based BP device) and PAT measured with wearable sensor in adult subject.

2. Study Hypothesis and Outcomes

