2.2. Outcome Measures

2.2.1. *Primary Outcome*

Primary outcome measures: Recorded measurements of BP as compared to the ICU standard of care monitoring, including both arterial line measurements and cuff-based measurements of the arm.

2.2.2. *Secondary Outcomes*

Secondary outcome measures: Recorded measurements of other physiologic signals such as HR, pain, temperature, cerebral blood flow, aEEG-like waveforms, and respiratory rate as compared to ICU standard of care monitoring. Accelerometry will be captured using these devices, and in a subset of study participants, will be compared to video recordings to validate the accuracy of these devices for detecting body position and movement (as these are known to affect BP measurement). Devices may also evaluate subjects' respiratory equipment. Questionnaire data examining parent opinions on use of wearable sensors compared to standard of care devices.

3. Study Design

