3.6. Study Procedures

Device application: In both the ICU and non-ICU study populations, standard-of-care devices will be used in all subjects and this data will be compared to that collected using novel wearable sensors suggested in this study. After participants are consented, multiple wearable sensors (up to 5) will be placed on the participant for the duration of the study. Multiple devices are required to estimate BP. One or more devices will be placed on the chest or back, and one or more additional devices will be placed peripherally (e.g. leg, foot, arm, hand, head, or ear). One or more additional devices may be placed on the patient's respiratory support device if applicable. Placing multiple devices will allow determination of which location provides the best signals in specific populations. These devices will be placed using a medical grade skin adhesive similar to the ones used in the ICUs, which will minimize the

risk of skin irritation or allergic reaction. Alternatively, we are currently testing a “soft wrap-around device” (similar to that currently used for blood pressure monitoring in the premature babies) with a sensor. The soft wrap-around device is composed of hypoallergenic cotton. Overlying this cotton, and not touching the subject’s skin, may include Coban wraps, paper tape, or a Velcro adhesion mechanism. Given the very small size of premature infant in the NICU, we may incorporate this new technology as needed in the NICU. In the ICU population, devices will be left in place for up to 72 hours, but will either be checked by the study or clinical team to ensure skin integrity and signal quality at least once every 24 hours. In the non-ICU population, devices will be left in place for up to 3 hours during a study visit to CAMP.

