Cuff-based blood pressure: While the wearable sensors are attached to participants in both the ICU and non-ICU populations, the participants will also be monitored with the normal standard of care monitoring montage. In addition, during one 3- or 4-hour period while the wearable sensors are attached to the patient, a member of the study team may take the participant’s BP using the ICU standard cuff-based method every 15 minutes. Cuff-based measures typically happen every 15-60 minutes for standard clinical care, depending on the stability of the patient and physician discretion. In the ICU population, if a standard clinical cuff-based BP measure is taken during the 15-minute time epoch, the clinical measurements will be used rather than obtaining a separate research measurement. Outside of this 3- or 4-hour window and for the remainder of the study duration in the ICU cohort, cuff-based BP measures will be made only as frequently as needed for standard clinical care.

Skin temperature: While the wearable sensors are attached to the participant, skin temperatures will be taken using a standard infrared thermometer. These measurements will be made at the same interval as the above cuff-based BP, over the same 4-hour period by a member of the study team. Outside of this 4-hour window, no skin temperature measures will be made for research purposes.

Device data: Wearable sensors can stream data continuously using near field communication (NFC) or Bluetooth technology. An encrypted laptop, iPad, or similar device will be left in the patient room and used to capture the continuous data stream from the wearable sensor. Additionally, wearable sensors can include onboard memory, and physiologic streams may be recorded to this onboard memory until transfer to an encrypted laptop for analysis.

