Standard of care data: In all participants where data from standard of care monitoring is captured and stored using the BedMasterEx system (all PICU and CCU beds, some NICU beds), and the Sickbay™ platform (CCU beds), this data will be used for comparison to data captured using EWP. In any participants where data are not captured and stored using the BedMasterEx system or Sickbay™ platform, video recordings will be made of the Phillips monitors using an encrypted mobile device. Within 48 hours, videos will be downloaded and transferred to a HIPAA secure server. In NICU patients without BedMasterEx data, the Somnostar system may be used to capture data for up to 4 hours of the study. All study data will be stored on an encrypted laptop and/or secure network for analysis. We will continue to follow patients for 5 years by collecting standard of care data entered into their electronic medical record.

Skin Integrity: Before and after wearable sensors are placed on the participant, the participant's skin integrity will be monitored using the ICU standard protocol, either the Braden Q scale (≥ 6 months of age) and/or Neonatal Skin Risk Assessment Scale (NSRAS; < 6 months of age). Additionally, a validated skin integrity scale will be used to score participants' skin condition at sensor placement site before sensor placement and immediately after sensor removal. At both of these time points, photographs may be taken of the participants' skin at the site of sensor placement to document any skin changes that occur during the period of wearable sensor wear. No faces will be photographed. One or more additional skin scores and photographs may be performed/taken between 30 minutes and 48 hours after sensor removal, as deemed necessary by the study and/or clinical team. The study team will consult the ICU bedside care team or CAMP clinical team within 1 hour for any concerning changes in skin integrity.

Questionnaires: After the study period ends, the parents may be approached to complete the questionnaires. These questionnaires will take less than 10 minutes to complete and are meant to assess opinions on use of these devices in the ICUs. These questionnaires will be completed using REDCap. If preferred, the family will complete a printed version of the REDCap questionnaire and this data will then be entered by study staff into the REDCap server. All questionnaire data will be stored on the secure REDCap server housed by Northwestern University.

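### Cuff readings are paired with the sensor epoch in which they were captured, with no exception for a sensor beyond the cuff on the same arm, where inflation may block or delay the pulse.

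*Protocol*

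**What the plan says.** The protocol's Section 5.2 divides continuous signals into 30-second epochs and states for cuff readings that "each measure will be matched and compared to the 30-second epoch during which the measure was captured". No exception follows.

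Section 2.2 defines the primary outcome as sensor blood pressure against standard monitoring, "including both arterial line measurements and cuff-based measurements of the arm". It does not name a side. Section 3.6 says that "Multiple devices are required to estimate BP". One or more devices go on the chest or back, and "one or more additional devices will be placed peripherally (e.g. leg, foot, arm, hand, head, or ear"). No relation between the sensor limb and the cuff limb is given.

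The estimation algorithm is not stated. The Figure 2 caption gives an example based on pulse arrival time (PAT): "Correlation of systolic blood pressure (measured with cuff-based BP device) and PAT measured with wearable sensor in adult subject".

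In one window of 3 or 4 hours the study team may measure pressure "using the ICU standard cuff-based method every 15 minutes". In the ICU, "if a standard clinical cuff-based BP measure is taken during the 15-minute time epoch, the clinical measurements will be used" in place of a research reading.

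**The concern.** Matching a cuff value to the sensor signal at the same moment is the natural choice for an agreement study. It has one weak spot. A cuff reading is obtained by inflating a cuff on the arm, so the epoch of capture may overlap inflation. A sensor on the forearm or hand beyond that cuff may then see a blocked or late pulse. If the pressure estimate uses pulse arrival time, as the Figure 2 example suggests, the reference method itself disturbs the test method in exactly the epoch used for comparison.

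Three results are exposed:

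- **Bias and limits of agreement.** By the protocol's background section, the cuff is the only pressure reference for ICU patients without an arterial line.
- **The per-person correlation.** A constant shift within a child would leave it unchanged, but a variable artefact would not.
- **The comparison of sensor sites.** Section 3.6 wants to learn which location gives the best signals. Cuff artefact, or values lost to it, could count against arm and hand sites for a reason that has nothing to do with the sensor.

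**Working it through.** The plan gives no figure on this point to reproduce. The check has three parts.

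**1. Which pairs are exposed.** The cuff is on an arm (Section 2.2). Chest, back, leg, foot, head, ear and opposite-arm sensors are not beyond it, nor is an arm sensor above the cuff on the same side. Exposed pairs come only from an arm or hand sensor beyond the cuff on the same limb. The arterial-line comparison does not use this pairing rule.

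**2. How many readings per child.** At one reading per 15 minutes, the window gives 3 × 60/15 = 12 or 4 × 60/15 = 16 readings at most. If cuff and sensor share a limb throughout, all 12 or all 16 window pairs for that sensor are exposed. For any sensor outside the exposed group the number is 0.

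**3. What exposure could do (illustration only).** Let p be the share of cuff pairs exposed, d the mean shift in those pairs, and s the SD of differences without artefact. Then

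- bias = p × d
- SD = √(s² + p(1 − p)d²)
- half-width of the limits = 1.96 × SD, centred on the bias

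The values of p, d and s are assumptions; the protocol gives none of them. With s = 6 mmHg, no exposure gives bias 0 and limits ±11.8. Bias is shown as a magnitude, since its direction is unknown.

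| p | d = 5: bias, limits | d = 10: bias, limits | d = 20: bias, limits |
|---|---|---|---|
| 5% | 0.25, ±12.0 | 0.5, ±12.5 | 1.0, ±14.5 |
| 10% | 0.5, ±12.1 | 1.0, ±13.1 | 2.0, ±16.6 |
| 25% | 1.25, ±12.5 | 2.5, ±14.5 | 5.0, ±20.6 |

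Worked cell (p = 10%, d = 10): SD = √(36 + 0.10 × 0.90 × 100) = √45 = 6.71, and 1.96 × 6.71 ≈ 13.1.

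Other baselines at p = 10% and d = 5 / 10 / 20:

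- s = 4 (clean limits ±7.8): ±8.4 / 9.8 / 14.1.
- s = 8 (clean limits ±15.7): ±16.0 / 16.7 / 19.6.

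If the shift is +d or −d equally often, the bias cancels but the spread does not: SD = √(s² + p d²). With p = 10%, d = 10 and s = 6 this is √46 = 6.78, with limits ±13.3.

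If cleaning removes half of a 10% share, 0.05/0.95 = 5.3% remains, close to the 5% row. If it removes all of it, or if a blocked pulse gives no value at all, these pairs add no bias but are lost from that site.

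**Existing safeguards.** Section 5.1 has the analyst clean sensor data and check cuff data, and Section 3.6 has signal quality checked daily. Neither names same-limb pairs. The lag check in Section 5.2 looks for time offsets between methods; a lost or distorted pulse is not such an offset. The multi-level model handles clustering. Without a limb variable, a child whose cuff and sensor share an arm throughout looks like a child with a different bias.

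**The case against.** The strongest reply is that cuff side belongs on a case report form or in a procedure manual, and these are not shown. The data list in Section 4.1 names broad categories, so its silence on limb does not show that limb goes unrecorded. This stands. A reader might infer that cuff side is not recorded and that the information is lost for good; the protocol does not support that. Sensor site is probably documented, since Section 3.6 scores "skin condition at sensor placement site before sensor placement and immediately after sensor removal". What remains is the analysis rule itself, which is written in the protocol without exception and would take in the affected pairs even if every limb were recorded.

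It can also be said that the harm needs a chain of events. An arm or hand site must be used, on the cuff limb and beyond the cuff. Inflation must fall materially within the matched epoch. The pulse must be disturbed enough to give a wrong value, and that value must survive cleaning. This also stands. The protocol does not say which moment of a reading counts as its capture, and the effect of inflation on a pulse beyond the cuff is general measurement reasoning, not protocol text. These points limit the size of the concern and the confidence in it. They do not give a reason to keep such pairs in the main analysis unmarked.

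In the research window the study team takes the non-clinical readings and may be able to choose the limb. For the clinical readings that replace them, it may not.

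**Conclusion.** The point holds in a limited form. The stated rule compares the cuff value with a sensor signal that the cuff itself may disturb, for any sensor beyond the cuff on the same arm, and no stated safeguard identifies those pairs. The size is unknown. In the illustration it runs from no effect (no exposed pairs) to a bias of 5 mmHg with limits of ±20.6 (25% exposed, shift 20 mmHg), all on assumed values.

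A reader might go further and conclude that the cuff comparison as a whole is invalid, or that the published bias will be wrong. The documents do not support this. Most permitted sites are unaffected, the algorithm is not given, and exposed pairs may be few or may be cleaned out. This is a change worth making, with medium confidence, and not a demonstrated error in the result.

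**What to change.** - **Record** limb, side and position relative to the cuff for each cuff reading (clinical readings where available) and for each arm or hand sensor, unless the forms already do so. Position is needed because limb and side alone would also catch a sensor above the cuff.
- **Main cuff-agreement analysis:** exclude only pairs from sensors beyond the cuff on the same limb, and report how many there are.
- **Sensitivity analyses:** include those pairs as matched, and separately match them to an epoch before inflation.
- **Unknown cuff side:** state in advance how such pairs are handled.
- **All other sensors:** keep the same-epoch match.

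The cost is a small addition to data capture, a short addition to Section 5.2 and the loss of some pairs. If information fell in proportion to pairs, excluding 5 / 10 / 25% would raise the standard error of the bias by a factor of 1/√(1 − p) = 1.026 / 1.054 / 1.155, about 3 / 5 / 15%. That figure is only a guide. Exclusion may remove whole child-sensor clusters, so under the planned multi-level model the loss depends on how many children are affected and not only on the share of pairs. A child whose only peripheral sensor is beyond the cuff in every reading would contribute to the sensitivity analyses but not to the main cuff analysis. If such pairs prove rare, the record will show it and little is lost.

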A current limitation of monitoring in the ICU is the lack of methods for continuous, non-invasive capture of blood pressure (BP). In critically ill patients, clinicians rely on intra-arterial BP monitoring (IA-BP), whereby a catheter is inserted into the umbilical or other central or peripheral artery to provide continuous BP measurements. However, IA-BP procedures are invasive and lead to complications, thereby escalating risks of infection, bleeding, and thrombosis, increasing discomfort, and reducing contact. Thus IA-BP is only utilized in the most critically ill patients and is typically discontinued within 1 week. In the rest of the ICU population, only periodic cuff-based BP (CB-BP) measurements are obtained. CB-BP recordings are captured periodically, can be difficult to obtain, are disruptive, especially during sleep, and are highly unreliable. The lack of real-time and continuous monitoring of hemodynamic signals impairs the clinical team's ability to detect and promptly respond to acute risks of decompensation, as well as obscuring longer-term patterns which may be sensitive markers of developing instability.

The purpose of this study is to develop biocompatible electronic devices that will allow continuous, non-invasive hemodynamic measurements in the ICU (see sample figure 1 below). Members of this research team have developed innovative, wireless devices capable of being

[figure not shown]

Figure 1: Example of wearable sensor developed by the [name] group

comfortably and continuously worn while recording diverse physiologic measurements. These devices have already demonstrated the capability to accurately capture hemodynamic measurements in healthy adult subjects (unpublished data, see figure 2 below). We propose to 1)

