3.2. Eligibility Criteria

3.2.1. *Inclusion Criteria*

Participants must be admitted to one of the three ICUs at Lurie Children's, admitted to the NICU at Prentice, or visiting CAMP with a parent or guardian. Anyone who satisfies one of these criteria and is under 18 years of age can participate.

3.2.2. *Exclusion Criteria*

Anyone with a skin abnormality that would potentially increase risk of device use will be excluded. Anyone 18 years or older will be excluded. In the ICU population, any patient or family determined by an attending physician or bedside care team to be too unstable (patient) or experiencing too much stress (family) will not be approached for recruitment.

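### Bias is fixed as a single average difference, so a sensor that compresses blood pressure changes can look nearly unbiased while reading high at low pressure

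*Protocol*

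**What the plan says.** Protocol section 2.2 gives the primary outcome as "Recorded measurements of BP as compared to the ICU standard of care monitoring", covering both the arterial line and the arm cuff. Section 5.2 sets the unit of comparison: "For continuous measures of physiology, 30 second epochs will be defined for each method for comparison".

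Section 5.2 then names two assessments of agreement. The first is Bland-Altman plots, summarised by "bias and precision, which reflect the mean or average difference between two methods and the variation in these differences, respectively". The second is correlation: "Our second method consists of individual correlations between methods assessed for each person". The correlation may be converted to shared variance.

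For formal inference the section moves to multi-level models, "which yield the same statistics discussed above but account for the fact that observations taken from the same patient are more related" than observations from different patients. It names no term for BP level, no bias by BP range and no slope of the difference on BP.

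The opening background says that current monitoring impairs the clinical team's "ability to detect and promptly respond to acute risks of decompensation". It presents the sensors, once validated, as a way to see clinically important changes as they occur.

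**The concern.** The text fixes the formal bias estimate as one constant: the difference averaged over epochs and children, adjusted for clustering. A constant describes the sensor well only if its error is the same at every BP level.

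A common failure of an indirect measurement is compression toward the mean: the sensor moves in the right direction but not far enough. It then reads high when BP is low and low when BP is high, and the two errors offset each other in the average. The hoped-for use is to recognise important changes in BP, so the error away from the child's usual level matters most, and the planned bias averages it out. Compression could be reported as negligible bias with somewhat wider scatter.

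**Working it through.** **The plan's own figures.** Section 5.2 gives no expected bias, SD or slope. Its only figure, power above 99%, concerns detecting associations and comes without inputs, so it can be neither reproduced nor applied to this point.

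**Model.** Let R be the reference BP, c its mean and b the tracking slope (1 = faithful). Sensor = c + b(R − c) + noise. Then:

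- difference (sensor − reference) = (1 − b)(c − R) + noise
- mean difference = (1 − b)(c − mean R) = 0 for any b
- expected error at D mmHg below c = +(1 − b)D
- SD of differences = √[((1 − b)·SDw)² + noise²]
- within-child r = b·SDw / √[(b·SDw)² + noise²]

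**Assumed inputs (none is in the protocol).** Within-child SD (SDw) 5 mmHg, noise SD 4 mmHg, normal distribution, so a child's 10th percentile lies 1.28 × 5 = 6.4 mmHg below usual.

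| Slope b | Mean difference | SD of differences | r | Error at 10th percentile | Error after 20 mmHg fall |
|---|---|---|---|---|---|
| 1.0 | 0 | 4.0 | 0.78 | 0 | 0 |
| 0.8 | 0 | √(1 + 16) = 4.1 | 0.71 | +1.3 | +4 |
| 0.6 | 0 | √(4 + 16) = 4.5 | 3/√(9 + 16) = 0.60 | +2.6 | +8 |
| 0.4 | 0 | √(9 + 16) = 5.0 | 0.45 | +3.8 | +12 |

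A 20 mmHg fall is 20/5 = 4 within-child SDs here, so the last column describes a rare event. With SDw 8 it is 2.5 SDs, and slope 0.6 gives r = 0.77 against 0.89 for a faithful sensor.

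**Limits of agreement at slope 0.6.** Overall: 0 ± 1.96 × 4.47, or −8.8 to +8.8 mmHg, against ±7.8 for a faithful sensor. After a 20 mmHg fall: 8 ± 1.96 × 4, or about +0.2 to +15.8 mmHg. The overall limits present as scatter an error that at this level is almost always in one direction.

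**Correlation.** It falls from 0.78 to 0.60 (shared variance 61% to 36%). A faithful sensor with noise SD 6.67 gives the same value: 5/√(25 + 44.4) = 0.60. So r alone cannot separate compression from noise or show direction.

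**Only falls under-tracked.** Under normality the mean difference is (1 − b)·SDw·0.399. At slope 0.6 and SDw 5 that is 0.4 × 5 × 0.399 = +0.8 mmHg. A simulation of 500 children with 500 epochs each (assumed between- and within-child SD 8, noise SD 3) gave, for slopes 0.8, 0.7 and 0.5, overall bias of +0.6, +1.0 and +1.6 mmHg, against +3.3, +4.9 and +8.3 mmHg in each child's lowest 5% of epochs.

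**Can the plot show it?** In the same simulation at slope 0.7, the pooled Bland-Altman slope was −0.30 when compression was around the population mean, −0.11 when it was around each child's own mean, and −0.03 when only falls were under-tracked. A faithful sensor gave about +0.03.

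**The pair mean as regressor.** The slope of the difference on the pair mean has the sign of Var(sensor) − Var(reference). At slope 0.6, SDw 5, noise SD 4 and negligible reference error, Var(sensor) = 9 + 16 = 25 and Var(reference) = 25. The slope is exactly zero despite real compression.

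**The case against.** The strongest reply is that a mean difference is the standard definition of bias, that nothing in section 5.2 forbids a level term, and that such detail usually sits in an SAP, which was not available here. The definition is indeed standard. But the protocol also says that the formal models return the same statistics, so an SAP following that sentence would estimate a constant.

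A second reply is that the planned outputs are not blind to compression. This largely stands. A reader might infer that correlation is unaffected by slope; with fixed noise it falls, as shown. Bland-Altman plots display the difference against BP level, and compression around the population mean could be seen. What remains is that no slope is estimated, and the pattern is faint on a pooled plot when compression is within each child. Section 5.2 also plans lagged regression plots, but to find time lags.

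A third reply is that exact cancellation is a special case. That stands: rises must be under-tracked as well as falls.

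Two further inferences go beyond the text. Detecting decompensation is the motivation and the hoped-for use; the stated study purpose is to develop devices for continuous non-invasive measurement. Not approaching patients judged too unstable does not show that low-BP epochs will be absent, and most epochs lie near a child's usual level in any case.

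**Conclusion.** The concern holds in a limited form. As section 5.2 words it, the formal bias estimate on the primary outcome cannot show error that changes with BP level. Under symmetric compression it is near zero; under one-sided compression it is small and positive. Either way it is well below the error at low BP.

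In the illustration at slope 0.6, zero overall bias goes with about +2.6 mmHg at a child's 10th percentile and +8 mmHg after a 20 mmHg fall. All SDs and slopes are assumptions; the masking follows from the algebra, while its size depends on them.

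A reader might infer that this sensor does compress BP, or that any sensor missing falls would be reported as exactly unbiased. The protocol supports neither: it gives no tracking slope and does not describe the calibration. The point is that the planned numerical summaries would not identify the fault if it were present.

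**What to change.** **Arterial-line pairs.** In the multi-level model already planned, let the difference depend on reference BP through two terms: the epoch's deviation from the child's mean (within-child) and the child's mean (between-child). Report the within-child tracking slope, with bias and limits of agreement at low, usual and high reference BP, beside the overall bias. Include the lowest observed range as well as each child's 10th percentile, which may lie only a few mmHg below usual. This treats arterial-line error as negligible, which should be stated.

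**Cuff pairs.** Do not rely on the pair-mean slope, which can be zero under real compression when sensor and cuff variances are equal. Regressing on the cuff reading has the opposite problem: with SDw 5 and an assumed cuff error SD of 4, a faithful sensor would show a slope of 25/(25 + 16) = 0.61. The background itself describes cuff readings as very unreliable. Report the level-dependent cuff result as supportive, with a sensitivity range for assumed cuff error.

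**Wording.** Amend section 5.2 so that the formal models are not limited to reproducing the overall mean difference.

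**Cost.** No new data, two model terms, the cuff sensitivity analysis and one more table. Estimates at low BP will be less precise and possibly less favourable to the device.
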